6.1.8 DOSE ADJUSTMENTS/MODIFICATIONS/DELAYS

Patients will remain on the dosage of Cemiplimab-rwlc throughout the course of study treatment. Dose reduction is not allowed. The dose will be held until the resolution of the adverse events as below.

Adverse events (AEs) are to be reported according to the National Cancer Institute Common Terminology Criteria for Adverse Events (NCI-CTCAE) version 5. Patients who experience grade ≥ 3 treatment-related toxicity (excluding laboratory abnormalities that are considered clinically insignificant) that is not otherwise specified in the protocol will be required to temporarily discontinue treatment with Cemiplimab-rwlc. Such patients may be considered for resumption of treatment once the toxicity resolves to grade 1 or baseline, or when the toxicity is stable and manageable through supportive/medical therapy (eg, grade 3 hypertension that can be controlled with addition of a second anti-hypertensive agent) per the CTCAE version 5.

Holding of treatment due to an AE or a missed visit if a patient is hospitalized is not a violation. If a patient is able to come in for a study visit according to the visit schedule, but does not receive Cemiplimab-rwlc, the visit should be entered into the database. The protocol assessments required at the visit (ie, labs, physical exam) should still be completed as far as possible and the data entered at the appropriate visit in the electronic case report form (CRF). If the patient is not able to come in for a study visit, according to the study schedule, the visit should be skipped. If a scan was missed as part of the skipped visit, the response assessment will be performed prior to resuming treatment and subsequent scans will be performed in line with the original schedule.

Upon occurrence of a study treatment-related event at any time on the study, resumption of treatment after resolution or stabilization of the condition is allowed at the discretion of the investigator if resuming treatment is thought to be in the best interest of the patient, with the exception of the following categories:

- Patients with events that require Cemiplimab-rwlc to be discontinued for more than 84 days from last scheduled dose.

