- Patients with grade ≥ 2 uveitis. Patients with grade 2 uveitis will generally be discontinued from study treatment, unless there is resolution to grade ≤ 1 AND discussion with and approval by the site principal investigators. All patients with grade ≥ 3 uveitis will be permanently discontinued from study treatment.

After other AEs, resumption of treatment may be at the initial dose level. A patient who does not

tolerate Cemiplimab-rwlc will be removed from the study. Refer to [Appendix 1](#) for additional management guidelines for immune-related toxicities.

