	Grade 2	Hold until <Grade 1. Resume at same dose.	
• GI consultation and endoscopy is recommended to confirm or rule out colitis for grade 2 diarrhea that persists >1 week or grade 1-2 diarrhea with rectal bleeding (additional guidelines for the treatment of persistent colitis are provided below).• Grade 2 diarrhea should be treated with the addition of oral diphenoxylate hydrochloride and atropine sulfate four times daily and budesonide 9 mg daily.• Grade 2 diarrhea with diffuse ulceration and bleeding seen on endoscopy may require oral steroids with prolonged taper and represent an increased risk for the development of bowel perforation. Consider prophylactic antibiotics for opportunistic infections.• When symptoms improve to Grade 1 or less, steroid taper should be started and continued over no less than 4 weeks.• In patients with Grade 2 enterocolitis, cemiplimab should be withheld and antidiarrheal treatment should be started. If symptoms are persistent for more than one week, systemic corticosteroids should be initiated (eg, 0.5 mg/kg/day of prednisone or equivalent). When symptoms improve to Grade 1 or less, corticosteroid taper should be started and continued over at least 1 month.
	Grade 3-4	Hold cemiplimab Discontinue if unable to reduce corticosteroid dose to ≤ 10 mg per day prednisone equivalent within 12 weeks of toxicity	
• In patients with Grade 3 enterocolitis, cemiplimab will be permanently discontinued and treatment with systemic corticosteroids should be initiated at a dose of 1–2 mg/kg/day of prednisone or equivalent. When symptoms improve to Grade 1 or less, corticosteroid taper should be started and continued over at least 1 month. Consider prophylactic antibiotics for opportunistic infections. For Grade 3–4 diarrhea (or Grade 2 diarrhea that persists after initial steroid treatment),
• Rule out bowel perforation. Imaging with plain films or computed tomography (CT) can be useful.• Consider consultation with gastroenterologist and confirmation biopsy with endoscopy.• Treat with intravenous (IV) steroids (methylprednisolone 125 mg) followed by high-dose oral steroids (prednisone 1–2 mg/kg once per day or dexamethasone 4 mg every 4 hours). When symptoms improve to Grade 1 or less, steroid taper should be started and continued over no less than 4 weeks. Taper over 6–8 weeks in patients with diffuse and severe ulceration and/or bleeding.

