	Grade 2	Discontinue cemiplimab if symptoms persist despite treatment with topical immunosuppressive	
 Evaluation by an ophthalmologist is strongly recommended. Treat with topical steroids such as 1% prednisolone acetate suspension and iridocyclitics. Discuss with and obtain approval from site PI prior to resumption once there is resolution to grade ≤1

		therapy and do not improve to Grade 1 within the retreatment period OR requires systemic treatment.	
	Grade 3-4	Discontinue cemiplimab.	
 Treat with systemic corticosteroids such as prednisone at a dose of 1-2 mg/kg per day. When symptoms improve to \leqGrade 1, steroid taper should be started and continued over no less than 4 weeks. Discuss with and obtain approval from site PI prior to resumption once there is resolution to grade \leq1
Hepatic events 
 Hepatitis Hepatitis, Autoimmune 	Grade 1-2	Withhold cemiplimab if there is a treatment-emergent concurrent elevation of ALT and bilirubin that corresponds to an upward shift of 2 or more grades in both parameters.	
 Monitor liver function tests more frequently until returned to baseline values.
	Grade 3-4	Withhold (and consider Discontinuation of) cemiplimab when AST or ALT >5.0 times ULN and/or total bilirubin >3.0 times ULN.	
 Consider appropriate consultation and liver biopsy to establish etiology of hepatic injury, if necessary. Treat with high-dose IV glucocorticosteroids for 24–48 hours. When symptoms improve to grade 1 or less, a steroid taper with dexamethasone 4 mg every 4 hours or prednisone at 1–2 mg/kg should be started and continued over no less than 4 weeks. If serum transaminase levels do not decrease 48 hours after initiation of systemic steroids, oral mycophenolate mofetil 500 mg every 12 hours may be given. Infliximab is not recommended due to its potential for hepatotoxicity. Several courses of steroid tapering may be necessary as symptoms may worsen when the steroid dose is decreased.

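### Appendix 1 contradicts Section 6.1.8 on restarting after Grade 3-4 uveitis, and its Grade 3-4 colitis row does not say which events are held and which are stopped for good

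*Combined protocol and SAP*

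**What the plan says.** **Uveitis.** Section 6.1.8 leaves resumption after a treatment-related event to the investigator, "with the exception of the following categories". Two categories follow: interruptions of more than 84 days, and uveitis of grade 2 or above. Within the second, grade 2 may resume after resolution to grade 1 or less "AND discussion with and approval by the site principal investigators". For higher grades the text is absolute: "All patients with grade ≥ 3 uveitis will be permanently discontinued from study treatment".

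In the Appendix 1 uveitis entries, the Grade 2 row carries the bullet "Discuss with and obtain approval from site PI prior to resumption once there is resolution" to grade 1 or less, which agrees with 6.1.8. The Grade 3-4 row tells the site to discontinue in its dosing cell and then carries the same bullet in its action cell.

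**Colitis events.** One Appendix 1 block covers bowel obstruction, colitis, microscopic colitis, hemorrhagic enterocolitis, GI perforation, necrotizing colitis and diarrhea. At Grade 3-4 the dosing cell begins "Hold cemiplimab Discontinue if unable to reduce corticosteroid dose to" and sets the limit at 10 mg/day prednisone equivalent within 12 weeks. The action cell of that row says "In patients with Grade 3 enterocolitis, cemiplimab will be permanently discontinued". It then gives work-up and steroid instructions for Grade 3-4 diarrhea, with no dosing instruction of their own.

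**The concern.** These cells decide whether a patient receives the drug again after severe immune-related toxicity. Section 2.1 says that safety in immunocompromised patients is unknown, and the trial runs at six sites. Two sites that each follow the text could treat the same event in opposite ways: one restarts after Grade 3 uveitis with its own PI's approval, and the other stops for good. The same can happen after Grade 3 enterocolitis, depending on which cell of the row is read. For Grade 4 enterocolitis the row names no permanent stop, so the more severe event could end up under the milder rule. What is at stake is the safety of an individual patient and consistent dosing across sites.

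**Working it through.** The point is textual, so the check sets the passages side by side. Arithmetic enters only for the size.

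**1. Uveitis, grade 3 or above.**
- Section 6.1.8: permanent stop for all such patients; resumption only for grade 2.
- Appendix 1, Grade 3-4 dosing cell: discontinue, without the word permanently.
- Appendix 1, Grade 3-4 action cell: resumption possible after resolution, with site-PI approval.
- Result: the action cell offers what 6.1.8 forbids. The dosing cell does not rescue the row, because the protocol also uses the verb for temporary stops: under 6.1.8, patients with other Grade 3 or higher related toxicity "will be required to temporarily discontinue treatment with Cemiplimab-rwlc".

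**2. Colitis events, Grade 3-4.**
- Dosing cell: hold, for every event listed in the block.
- Action cell: permanent stop for Grade 3 enterocolitis; Grade 4 enterocolitis not named.
- Result: for Grade 3 enterocolitis the two cells give different instructions.
- Comparison with Grade 2: the dosing cell says hold, and the action cell says "In patients with Grade 2 enterocolitis, cemiplimab should be withheld and antidiarrheal treatment should be started". Those agree, so the conflict is confined to Grade 3-4.

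**3. Does other text settle it?**
- The introduction to Appendix 1 calls the appendix guidance and points to 6.1.8 for details on resumption. Section 6.1.8 points back to Appendix 1 for further management guidelines. For uveitis, 6.1.8 gives a clear answer. For enterocolitis it gives none, because enterocolitis is not among its exceptions to discretionary resumption.
- Section 5.4.1 says that participants with a treatment-related Grade 4 AE can be removed. That is permissive.
- Section 8.4.2 sends SAEs to the PI within 24 hours, but 8.4.1 limits reports to the PI to SAEs, so a Grade 3 event that meets no seriousness criterion would not trigger it.
- Section 8.5 halts the study after three probably related Grade 3 AEs. It does not govern rechallenge of one patient.
- The 84-day limit restricts late resumption only.

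**4. Size.** Inputs: n = 27 (Section 10.5) and colitis listed at 1% or less (Section 2.3.1, uncommon but serious).
- Expected cases: 27 × 0.01 = 0.27.
- Chance of at least one: 1 − (1 − 0.01)^27 = 1 − 0.99^27 = 0.238.

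Both are upper limits at the listed rate. They count colitis of any grade, whereas the conflict concerns Grade 3-4 enterocolitis. No rate is listed for uveitis.

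**5. Effect on the design.** Section 10.5 uses n = 27, P0 = 0.15 and P1 = 0.15 + 0.18 = 0.33. An exact binomial test that declares success at 7 or more responses gives alpha 0.0986 and power 0.838, which match the plan's 0.0986 and 83.8%. None of these inputs comes from the toxicity tables.

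**The case against.** The strongest case against: Appendix 1 is guidance, and on resumption it sends the reader to 6.1.8, whose uveitis rule could not be clearer. The stray bullet is probably a carry-over from the Grade 2 row. In the colitis row, a specific instruction would naturally override a general one: stop for Grade 3 enterocolitis, and hold for the rest, mainly diarrhea.

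Part of this stands. The colitis row is unclear drafting that admits a sensible reading, so it is a weaker case than uveitis. But the reading is not written down, and the dosing cell covers all seven listed event types. The pointer to 6.1.8 helps for uveitis only, and even there a site working from the table would still find a route to restart.

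A reader might go further than the documents allow in four ways:
- **A blanket rule that 6.1.8 governs would solve everything.** It would settle uveitis, but it would leave enterocolitis to discretionary resumption.
- **Grade 4 enterocolitis is meant to be held.** The text leaves it unnamed; that does not show intent.
- **The renal Grade 3-4 row is a third contradiction.** It pairs discontinue with a possible restart, but no text there requires a permanent stop, and the protocol also uses the verb for temporary ones. It is a question for the sponsor.
- **The chance of an affected patient is well above 23.8%.** That would need a uveitis rate, or a higher colitis rate in this population, and the documents give neither.

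**Conclusion.** The uveitis conflict is definite: the Grade 3-4 row of Appendix 1 is wrong as written and should match 6.1.8. The colitis conflict is real but limited. Grade 3 enterocolitis has two instructions in one row, Grade 4 enterocolitis is unnamed, and the reading that would reconcile the cells is left for the site to supply.

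Few if any of the 27 patients are likely to be affected. The figures of 0.27 expected cases and a 23.8% chance of at least one assume that the listed colitis rate carries over. That rate is not specific to immunocompromised patients, so the true figure could be higher here; restriction to Grade 3-4 enterocolitis would lower it.

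This is an internal inconsistency of minor severity. A reader might infer a flaw in the trial's design or in its primary result, but the documents do not support that: alpha, power, sample size and the primary analysis are untouched. It deserves correction because the harm to one patient could be serious and the remedy is a few words.

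**What to change.** 1. **Uveitis, Grade 3-4 row.** Delete the resumption bullet. Change the dosing cell to *Permanently discontinue cemiplimab*.
2. **Colitis events, Grade 3-4 row.** Split the dosing cell: *Grade 3 or higher enterocolitis: permanently discontinue. Grade 3-4 diarrhea without enterocolitis: hold; discontinue if steroids cannot be reduced to ≤10 mg/day prednisone equivalent within 12 weeks.* Name Grade 4 in the enterocolitis bullet. The present text does not state a permanent stop for Grade 4, so the sponsor's clinicians should confirm it. They should also assign the other listed events explicitly (colitis, microscopic colitis, necrotizing colitis, GI perforation, bowel obstruction). None of these should fall under hold by default.
3. **Section 6.1.8 exception list.** Add *any event for which Appendix 1 or Table 4 requires permanent discontinuation*. Grade 4 skin events and Grade 3-4 infusion reactions are already permanent stops that 6.1.8 does not list.
4. **Renal events, Grade 3-4 row.** Ask the sponsor to confirm whether restart is intended; change the text only if it is not.

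The cost is an amendment to a few table cells and one line of 6.1.8, plus a letter to sites. It adds no procedures or patients.

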APPENDIX

APPENDIX 1: MANAGEMENT ALGORITHMS

These general guidelines constitute guidance to the Investigator and may be supplemented at the discretion of the treating physician. The guidance applies to all immuno-oncology agents and regimens.

A general principle is that differential diagnoses should be diligently evaluated according to standard medical practice. Non-inflammatory etiologies should be considered and appropriately treated.

Corticosteroids are a primary therapy for immuno-oncology drug-related adverse events. The oral equivalent of the recommended IV doses may be considered for ambulatory patients with low-grade toxicity. The lower bioavailability of oral corticosteroids should be taken into account when switching to the equivalent dose of oral corticosteroids.

Consultation with a medical or surgical specialist, especially prior to an invasive diagnostic or therapeutic procedure, is recommended.

The frequency and severity of the related adverse events covered by these algorithms will depend on the immuno-oncology agent or regimen being used.

Patients will not be able to resume treatment following events that require Cemiplimab-rwlc to be discontinued for more than 84 days (12 weeks) from last scheduled dose. Reference the Dose Adjustments/Modifications/Delays section for additional details.

Events	CTCA E v5 Grade	Management /Cemiplimab Dosing	Action/Supportive Care Guidelines
Colitis events 
• Bowel obstruction• Colitis• Colitis microscopic• Enterocolitis hemorrhagic• GI perforation• Necrotizing colitis• Diarrhea: All patients who experience diarrhea should be advised to drink liberal quantities of clear fluids. If sufficient oral fluid intake is not feasible, fluid and electrolytes should be substituted via IV infusion.	≤Grade 1	No change in dose	
• For diarrhea, treat symptomatically (loperamide, oral hydration, electrolyte substitution and ADA colitis diet). Endoscopy is recommended if symptoms persist.• Grade 1 diarrhea that persist for >1 week should be treated with the addition of oral diphenoxylate hydrochloride and atropine sulfate four times daily and budesonide 9 mg daily.

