Grade 3-4	Discontinue cemiplimab	
 Consider pulmonary function tests with pulmonary consult. Bronchoscopy with biopsy and/or BAL is recommended. Treat with IV steroids (2-4 mg/kg per day prednisone or equivalent). When symptoms improve to grade 1 or less, a high-dose oral steroid (1-2 mg/kg prednisone once per day or 4 mg dexamethasone every 4 hours) taper should be started and continued over no less than 4 weeks. Add prophylactic antibiotics for opportunistic infections. If IV steroids followed by high-dose oral steroids does not reduce initial symptoms within 48-72 hours, treat with infliximab at 5 mg/kg once every 2 weeks. Discontinue infliximab upon symptom relief and initiate a prolonged steroid taper over 45-60 days. If symptoms worsen during steroid reduction, initiate a retapering of steroids starting at a higher dose of 80 or 100 mg followed by a more prolonged taper and administer infliximab. 	
Renal events 
NephritisNephritis autoimmuneRenal failure	Grade 1	Consider withholding Cemiplimab if event does not improve with	
 Provide symptomatic treatment. Monitor creatinine weekly; when it returns to baseline, resume routine creatinine monitoring per protocol.

 Renal failure, Acute 		symptomatic treatment.	
	Grade 2	Consider withholding Cemiplimab.	
 Systemic corticosteroids at a dose of 1–2 mg/kg/day of prednisone or equivalent may be indicated. When symptoms improve to Grade 1 or less, corticosteroid taper should be started and continued over at least 1 month. Consider prophylactic antibiotics for opportunistic infections. Consider renal biopsy. If elevations persist >7 days or worsen, treatment as Grade 4.
	Grade 3-4	Discontinue cemiplimab	
 Renal consultation with consideration of ultrasound and/or biopsy as appropriate. Monitor creatinine daily. Treat with systemic corticosteroids at a dose of 1–2 mg/kg prednisone or equivalent once per day. When symptoms improve to grade 1 or less, steroid taper should be started and continued over no less than 4 weeks. Discontinue cemiplimab if unable to reduce corticosteroid dose for irAEs to ≤10 mg. Cemiplimab treatment may be restarted if symptoms resolve.

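### Appendix 1, renal events: the Grade 3-4 row gives conflicting stop and restart instructions for cemiplimab, and persistent Grade 2 events are sent to that row without saying whether dosing is included

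*Combined protocol and SAP*

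**What the plan says.** Each renal row in Appendix 1 has a dosing cell and an action cell.

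- **Grade 2, dosing cell:** "Consider withholding Cemiplimab". No duration is given.
- **Grade 2, action cell:** corticosteroids may be indicated, biopsy is to be considered, and then: "If elevations persist >7 days or worsen, treatment as Grade 4".
- **Grade 3-4 (one shared row), dosing cell:** "Discontinue cemiplimab". No condition is attached.
- **Grade 3-4, action cell:** after the consultation, monitoring and corticosteroid instructions come two sentences on cemiplimab: "Discontinue cemiplimab if unable to reduce corticosteroid dose for irAEs to ≤10 mg", followed by "Cemiplimab treatment may be restarted if symptoms resolve".

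The protocol body adds three relevant statements.

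- **Section 6.1.8, general rule:** after a treatment-related event, "resumption of treatment after resolution or stabilization of the condition is allowed at the discretion of the investigator". The exceptions listed are more than 84 days off drug and uveitis. Renal events are not among them.
- **Section 6.1.8, Grade 3 or higher:** patients with a treatment-related toxicity for which the protocol gives no specific instruction "will be required to temporarily discontinue treatment with Cemiplimab-rwlc".
- **Section 5.4.1:** a treatment-related Grade 4 event is one of the reasons for which the investigator or funder can remove a participant.

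**The concern.** A site with a Grade 3 or 4 renal event finds an unconditional stop in one cell. The next cell has a conditional stop and a permission to restart. Both cannot be followed if the unconditional stop is meant to be final, and the row does not say whether it is.

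A persistent or worsening Grade 2 event reaches the same row through the escalation sentence. Two questions are then open: whether the escalation applies to cemiplimab at all, and if so, which of the two Grade 3-4 instructions applies.

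What is at stake is safety and consistency of exposure. Six sites enrol (Study Summary). Section 5.1 admits patients with creatinine clearance just above 30 mL/min and patients with multiple myeloma, and creatinine is in the laboratory panel drawn each cycle. Toxicity is a secondary endpoint, and drug exposure is to be summarised under section 10.4.4. The same laboratory course could lead to different dosing at different sites, with each site able to point to a printed instruction.

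**Working it through.** There is no planned figure to reproduce. The check is a comparison of the texts, plus one line of arithmetic on doses.

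**Step 1. Can both Grade 3-4 cells be followed?** There are two ways to read the dosing cell.

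- *Final stop.* The restart sentence in the action cell then contradicts it, and the conditional discontinuation is redundant because the drug has already been stopped.
- *Temporary stop.* The restart sentence fits. The conditional sentence must then use the same verb for something more lasting, or it adds nothing. One word carries two meanings within one row.

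Neither reading leaves all three statements with a consistent meaning.

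**Step 2. Does usage elsewhere settle the word?** It points both ways.

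- *For temporary:* section 6.1.8 speaks of temporary discontinuation, and the Appendix 1 preamble bars resumption only after "events that require Cemiplimab-rwlc to be discontinued for more than 84 days (12 weeks) from last scheduled dose". Skin Grade 4 spells out that the stop is permanent; the renal cell does not.
- *For lasting:* the Appendix 1 tables treat holding or withholding as a different action from discontinuing. The hepatic Grade 3-4 dosing cell names both, one as an instruction and one as something to consider. The colitis Grade 3-4 dosing cell orders a hold and then discontinuation if steroids cannot be reduced, so there the steroid condition follows a hold. The uveitis Grade 3-4 dosing cell has the same bare instruction as the renal one, and section 6.1.8 makes that stop permanent.

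**Step 3. Does the protocol body settle it?**

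- The temporary-stop rule for Grade 3 or higher in section 6.1.8 covers only toxicities without their own instruction. Renal events have one.
- The general resumption rule in section 6.1.8 does not exclude renal events, so it supports restart against the dosing cell.
- Section 5.4.1 allows removal for a treatment-related Grade 4 event, in permissive wording.

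The body text adds statements to be reconciled and does not decide between the cells.

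**Step 4. What does the Grade 2 escalation cover?** Its target can only be the shared Grade 3-4 row, because there is no separate Grade 4 row. That row uses the idea of treatment in both senses: treating with corticosteroids, and cemiplimab treatment that may restart. For a Grade 2 elevation on day 8, the readings are:

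| Scope of the escalation | Reading of the Grade 3-4 row | Result for cemiplimab |
|---|---|---|
| Steroid and supportive care only | not applicable | Grade 2 dosing cell still governs: continue or withhold |
| Includes dosing | Restart sentence governs | Stop, then possible resumption within 84 days |
| Includes dosing | Dosing cell is final | No further doses |

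**Step 5. Size for one patient.** Section 6.1.9 plans 17 cycles, one dose per cycle. For an event after dose 4, taken as an illustration, 17 − 4 = 13 doses remain. The range is therefore 0 to 13 doses lost. The upper end depends on the final-stop reading. The 84-day limit on resumption equals 84 / 21 = 4 cycle lengths.

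**Step 6. Frequency.** The documents give no rate for renal events of any grade. Section 2.3.1 lists nephritis only among potential immune-related effects, without a figure. No probability that the trial meets the conflict can be derived.

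**The case against.** The best defence is that the row can be read in order: stop, treat, restart if the event resolves, and stop for good if steroids cannot be reduced. The protocol does use the verb for reversible stops, says so where it means a permanent one, and in section 6.1.8 allows resumption after related events without excluding renal ones. This is a plausible account of what was intended. It still needs one word to change meaning between adjacent cells, and the hold-versus-discontinue distinction elsewhere in Appendix 1 allows a site to defend the other reading.

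Appendix 1 also calls itself guidance that the treating physician may supplement. That lessens the problem, but freedom to supplement does not tell a site which of two opposing printed instructions applies, and section 6.1.8 refers sites to the appendix.

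It can further be said that the rows concern drug-related events and that the preamble asks for non-inflammatory causes to be considered. A creatinine rise attributed to myeloma or to low clearance at entry may therefore fall outside them. This stands: the eligibility criteria make renal elevations foreseeable, but they do not show how often these rows would apply.

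A reader might infer a separate contradiction within Grade 2, between the discretionary dosing cell and the escalation after 7 days. The text does not support that. The dosing cell sets no duration, so the two cells read as a default followed by an escalation. What is missing is the scope of the escalation.

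**Conclusion.** The point holds as an internal inconsistency in the renal Grade 3-4 row, with an ambiguity of scope in the Grade 2 row that leads into it. It is wrong as written and should be corrected, because it leaves opposing stop and restart instructions for the same renal event.

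For a single persistent Grade 2 event, the consequence ranges from no missed dose to all remaining doses. The upper end assumes that the escalation covers dosing and that the stop is final; the renal row states neither. Across the trial the size is unknown, since any figure for the number of patients affected would rest on an assumed rate.

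A reader might also infer that the efficacy result is compromised. The documents do not support this. The one-sided exact test and the sample size of 27 in section 10.5 use nothing from this row. Under sections 5.4.2 and 7.3.5, patients who stop early are still followed for response until progression and for survival. The effect is on patient management, on exposure and on how uniformly toxicity is handled across sites. No view is taken on which clinical rule is right.

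**What to change.** Edit the renal rows of Appendix 1 so that:

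1. the Grade 3-4 dosing and action cells give one consistent instruction, stating whether the stop is temporary or permanent and whether, and on what condition, restart is possible;
2. the Grade 2 escalation sentence states whether it governs cemiplimab dosing or only corticosteroid and supportive care, and names the row as it is labelled (Grade 3-4);
3. the result agrees with the resumption rule and its exceptions in section 6.1.8, and with the Grade 4 removal reason in section 5.4.1.

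The clinical team decides the content. The cost is one table edit, with a matching sentence in section 6.1.8 or 5.4.1 if the chosen rule needs it, submitted for IRB approval as section 13.2 requires for any amendment. No change to the sample size, the primary analysis or data collection is needed.
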